3. Study Design

This study is a single-center, prospective, non-blind, parallel-group, randomized controlled trial with an active comparator.

4. System technical specifications

The version of SWORD Phoenix used in this study is composed of the following components:

- a) **Inertial motion trackers:** each one is composed of a three-axis gyroscope, three-axis accelerometer and a three-axis magnetometer, allowing 3D

Version 2.0

Date: 06/14/2018

movement analysis and quantification. The trackers communicate via Bluetooth LE with a tablet computer.

- b) **Mobile App:** a mobile app that processes the information generated by the motion trackers and provides real-time biofeedback regarding movement quality and patient performance.
- c) **Web-based Portal:** a web-based platform that allows the clinical team to prescribe motor tasks and monitor results.

Motion Trackers

The motion trackers are placed on body segments using Velcro® straps. Each motion tracker is placed in a specific position. To assist in the correct placement of the motion trackers, both the trackers and the matching straps are color-coded. In this study, the following setup will be used:

- **Red tracker:** over the sternal manubrium
- **Green tracker:** on the medium third of the external surface of the upper arm, pointing to the elbow
- **Blue tracker:** on the dorsal surface of the distal third of the forearm, pointing to the hand

Mobile App

The mobile app guides the patient in each exercise session. Before each exercise, the

patient is presented with a real-life video and audio explanation of that exercise. The execution interface is subsequently shown. This screen features: a) a posture dummy indicating correct/incorrect posture; b) a progress bar; c) a timer indicating rest time between repetitions and prompting start when rest time is over; d) a repetition counter; e) a star counter and f) a timer displaying time left to complete the exercise.

Only correctly performed repetitions count towards the repetition counter. A correct repetition is defined as a movement starting at the baseline and reaching or surpassing the specified target, without violating movement or posture constraints. In case the patient violates a movement constraint, a message is prompted showing which movement error was performed, so that the patient can correct the movement in the following attempts.

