For each correct repetition, the patient earns from 1 to 3 stars, depending on how much he was able to surpass the target, as long as he has not violated any movement or posture constraints.

Web Portal

The portal is a web-based platform that allows the clinical team to create new patient profiles and create exercise sessions for each patient. When a patient performs a session, the results are uploaded to the platform and available for review. Based on this information, the clinical team can edit the parameters of each session and exercise according to patient performance and progress.

5. Study Outcomes

The assessment of the effectiveness of treatments in shoulder conditions is complex^{49,50} and should include not only the traditional clinical outcomes, such as

joint measures, but also the assessment of functional deficits, through patient reported outcome measures.⁴⁹⁻⁵¹ Lately, there has been a shift towards the latter, which are currently the primary outcomes of most research studies.⁴⁹

The Constant Shoulder Score is one of the most used outcome assessment tools worldwide,^{49,50,52,53} maybe due to the fact that it's psychometric properties have been widely studied,⁵⁰ and that it includes essential measures - physical assessment of strength and motion - as well as patient-reported function.^{49,52,53} Additionally, it is considered, in some studies, as a gold standard or "reference scale",⁵¹ and its extensive use allows for comparisons between study samples and results.⁴⁹

The DASH questionnaire also provides a very accurate assessment⁵¹ and has been recommended to be the first line of assessment in shoulder disorders, due to its high responsiveness and well-established benchmarks.⁵² The QuickDASH, its short version, with 11 items, is also validated, and its psychometric properties are very high and similar to the original long version.^{52,54} The use of QuickDASH was analysed in patients with a rotator cuff repair and was recommended to assess patients who underwent a surgery process,⁵⁴ therefore applicable in the present context.

Although the use of patient-reported outcome measures is highly recommended, conventional measures such as range of motion are still clinically relevant and critical part of shoulder assessment.^{17,52} Shoulder flexion, abduction, internal and external rotations are the mainly cited movements, although with high variability in the positions of measure.⁵²

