5.2 Secondary outcomes

The secondary outcomes will be:

- The change in patient reported function in comparison to the baseline, measured by the QuickDASH score
- The change in shoulder range of motion in comparison to the baseline, measured by the shoulder flexion degree in a sitting position (in degrees)

6. Sample size estimate

Sample size estimation was performed taking into consideration the primary outcome measure – The Constant Score - and a non-inferiority scenario.

In the absence of similar studies, the calculations were made taking into account the study by Arndt *et al.* (2012)⁴⁰. This was a large study (n=100 patients) which compared two different rehabilitation protocols after ARCR and which used the same primary outcome as our study. In this study, the standard deviation of the Constant

Score at baseline was 12.0. A Minimal Clinically Important Difference (MCID) of 10.4 was considered, based on the study by Constant *et al.* (2008).⁵⁵

Considering a power of 90%, a two-sided 0.05 significance level and a 10% dropout rate, 68 patients would be necessary to detect a 10.4 points difference between the two groups.

7. Location of Recruitment

Patients will be recruited at Hospital da Prelada - [name] da Cruz.

8. Inclusion criteria

- a) Patients over 18 and under 70 years old
- b) Shoulder pain and functional limitation with clinical examination compatible with reparable rotator cuff tear
- c) Imaging (MRI or ultrasound) evidence of rotator cuff tear (supra and/or infraspinatus tendon tear inferior to 5cm)
- d) Indication for a rotator cuff repair according to the patient's orthopedic surgeon
- e) Ability to understand simple and complex motor commands
- f) Availability of a carer to assist the patient after surgery

9. Exclusion criteria

Preoperative

- a) Patients with indication for revision cuff repair
- b) Complex cuff tears (involving subscapularis tendon or more than one tendon besides supra and infraspinatus, or massive dimension tears)

- c) Glenohumeral arthritis
- d) Irreparable tendon defect
- e) Patients with concomitant neurological disorders (ex. Stroke, Parkinson's disease, multiple sclerosis)
- f) Aphasia, dementia or psychiatric comorbidity interfering with the communication or compliance to the rehabilitation process
- g) Respiratory, cardiac, metabolic conditions or others incompatible with at least 30 minutes of light to moderate physical activity

Postoperative

- h) Irreparable tendon lesion

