13.1.3 Shoulder range of motion

The shoulder range of motion will be measured in the sitting position.

The system used in the study is a validated medical device for joint angle measurement. Therefore, shoulder range of motion will be measured automatically

SH-RCT-ARCR-01 Study Protocol

by the system.

In this study, active range of motion will be measured in the following movements:

- a) Elevation of the shoulder in the scapular plane, sitting: with the patient sitting, with the arm fully extended, have the patient actively raise the arm in the scapular plane as much as possible, with extended elbow.
- b) Sitting shoulder flexion: with the patient sitting, with the arm fully extended, have the patient actively raise the arm as much as possible, with extended elbow.
- c) Sitting Shoulder Abduction: with the patient sitting, with the arm as close as possible to the body, have the patient actively open the arm as much as possible, with extended elbow.
- d) Sitting Shoulder External Rotation: with the patient sitting with 90° bent elbow and hand pointing forward, have the patient actively rotate the arm outwards, as much as possible.

In order to achieve this, the investigator will need to:

- 1) Create a new patient in the Phoenix Portal
- 2) Prescribe these four different exercises, described above
- 3) Setup SWORD Phoenix
- 4) Ask the patient to perform five repetitions of each movement to the best of his ability, while SWORD Phoenix records movement parameters
- 5) After the session, login to the Portal, go to the session's results and click on detailed results for each exercise. Record the value of best repetition for each exercise in the patient file.

13.2 Assessments at 6, 12, 16, 20 (and/or 24) weeks after surgery and assessment

12 months after surgery

These assessments will include:

- a) Constant score
- b) QuickDASH
- c) Shoulder range of motion (as described for the baseline assessment)

14. Intervention

Both study groups will receive early-onset home-based rehabilitation for 20 weeks, starting two weeks after surgery.²⁸ This program can be extended for another 4 weeks if necessary.

The experimental group will perform daily home-based rehabilitation sessions using SWORD Phoenix, under remote monitoring by a physiotherapist, as well as home one-to-one physiotherapy sessions, with decreasing periodicity depending on program stage.

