The conventional rehabilitation group will receive home-based rehabilitation provided by a physiotherapist, 3 times a week, for 1 hour. Patients will also be instructed to perform additional unsupervised sessions in at least two other days of the week. Compliance to these additional sessions is not mandatory, but patients will be asked to fill in a diary regarding these extra-sessions.

The intervention arm, additionally to the one-to-one sessions, will perform daily home-based rehabilitation sessions using the system alone, under remote monitoring

SH-RCT-ARCR-01 Study Protocol

by a physiotherapist. Patients will be instructed to perform exercise sessions at least 5 times per week, but compliance to that frequency is not mandatory per protocol. The number of sessions, daily adherence and total training time will be registered automatically by the system and will be made available through the Web Portal, from where it can be transcribed to each patient file. When required, additional visits or telephone calls for technical assistance can be performed by the physical therapist. These will be registered as such in the patient file.

In the absence of a gold standard, the rehabilitation protocols were designed taking into account: a) a recent systematic review on the subject;⁴ b) a review of the concepts and evidence-based guidelines on this subject by van der Meijden *et al.* (2012)¹⁵; c) an overview of systematic reviews comparing early and conservative rehabilitation²⁸ and d) the protocol of the Massachusetts General Hospital for rehabilitation after rotator cuff repair.

The rehabilitation program will be based on the principles outlined in the following tables 1-4. In any case, these protocols can be tailored to the patient's specific needs, according to the assessment of the orthopedic surgeon and the physical therapist.

Table 1. Immediate Post-op Phase

Rotator cuff repair program: Immediate Post-op Phase (weeks 0 to 2) - Immobilization period	
Goals	Precautions
Control pain and swelling	
Protect the rotator cuff repair	Do not lift the operated arm
Protect wound healing	
Prevent shoulder stiffness	
Intervention	
Conventional PT group	Experimental Group
Use of a sling during the day and during the night until week 4	
Ice pack application to the operated shoulder for 15 minutes if necessary to reduce pain and swelling several times per day	
Promote the active movement of fingers, hand and elbow to increase circulation	

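### Shoulder flexion is measured on the device that only the experimental arm uses at home, and Section 13.1.3 does not keep the app's targets, stars and feedback out of the patient's view

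*Combined protocol and SAP*

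**What the plan says.** Section 5.2 names change in sitting shoulder flexion as the range-of-motion secondary outcome, and Section 16 compares the arms on change from baseline to week 20. Section 13.1.3 states that "shoulder range of motion will be measured automatically" by the study system. Its second step for the investigator reads "Prescribe these four different exercises, described above". The patient then makes five repetitions of each movement, and the investigator reads the results later in the portal: "Record the value of best repetition for each exercise in the patient file". Section 13.2 applies the same method at every follow-up.

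Section 4 says that the app "provides real-time biofeedback regarding movement quality and patient performance". The screen includes a posture figure and a star counter, and "the patient earns from 1 to 3 stars, depending on how much he was able to surpass the target". A repetition counts only if it reaches the target without breaking a movement or posture constraint.

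Section 14 gives the device to one arm: "The experimental group will perform daily home-based rehabilitation sessions using SWORD Phoenix". It adds "Patients will be instructed to perform exercise sessions at least 5 times per week", and makes that frequency non-compulsory. Shoulder Flexion is on the Phoenix exercise list in the Phase 3 and Phase 4 tables. The conventional arm progresses to active flexion in Phase 3 with a physiotherapist and has no device in its programme.

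**The concern.** The measuring instrument for a named outcome is also the experimental treatment. If an assessment looks to the patient like an ordinary Phoenix session, experimental patients come to it knowing the interface, its constraints and the reward for going past the target. Control patients see it only at study visits. A patient who knows how the app responds may push further, or may lose fewer repetitions to constraint violations, without having more shoulder motion.

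Part of an observed flexion advantage at week 20 could then reflect familiarity with the test. The sponsor's own device would have produced the reading, so this alternative explanation would be an obvious one to raise.

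**Working it through.** The plan states no figure for this outcome: no SD, margin or expected difference in degrees. The check is therefore mainly a comparison of sections.

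**Exposure to the interface**
- Both arms: assessments before surgery and at weeks 6, 12, 16 and 20 (Section 13). That is four visits before week 20, so 4 × 5 = 20 recorded flexion repetitions each.
- Experimental arm only: home Phoenix sessions, with Shoulder Flexion listed from Phase 3, which starts between weeks 8 and 10. At week 6 only general device familiarity can differ. At weeks 12, 16 and 20 familiarity with the flexion exercise can differ too.

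**Whether an existing safeguard removes the difference**
- Device validation (Section 13.1.3) concerns the accuracy of the angle. It does not bear on how hard or how skilfully the patient performs.
- Assessor blinding (Section 12) does not act on an effect that works through patients, who know their group.
- Change from baseline (Section 16) does not cancel it, because the unequal exposure begins after baseline.
- Section 13.1.3 does not say what the patient sees during assessment, whether a target is set, or whether the best repetition is chosen only from those the app counts as correct.

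**Illustration in SD units (assumed, not taken from the documents)**

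Suppose there is no true difference and familiarity adds a spurious gain of b SD to the experimental arm. Assume normal data, equal SDs and a two-sided 5% t test, with n per arm.

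Noncentrality = b / √(2/n), with 2n − 2 degrees of freedom. The chance of significance is P(|T| > t₀.₉₇₅).

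The planned total of 68 gives n = 34. After 10% dropout, 68 × 0.9 / 2 = 30.6, taken as 30. For b = 0.2 and n = 34, noncentrality = 0.2 / √(2/34) = 0.2 / 0.2425 = 0.82.

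| Assumed b (SD) | n = 34 | n = 30 |
|---|---|---|
| 0 | 5.0% | 5.0% |
| 0.1 | 6.9% | 6.7% |
| 0.2 | 12.8% | 11.9% |
| 0.3 | 23.0% | 20.8% |
| 0.5 | 52.9% | 47.8% |

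From 0.2 SD upward, nearly all of these results favour the experimental arm (12.6 of the 12.8 percentage points at b = 0.2, n = 34). The table shows what a bias of a given size would do. It is not evidence that such a bias exists.

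**The case against.** The strongest reply is that Section 13.1.3 does not say feedback is shown at assessment. It describes patients making their best effort while the system records, with values read afterwards in the portal. The test itself is simple: raise the arm as far as possible. Instructions, instrument and scoring are the same in both arms, and the assessor is blinded. Controls also train active flexion and will have done the test at four earlier visits. Keeping the best of five may even help an unfamiliar patient, since the early repetitions serve as practice.

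Much of this stands, and it rules out several stronger readings that a reader might infer:
- *That patients are shown targets and stars during assessment.* Running the movements as prescribed exercises makes this plausible, but no section says so.
- *That the experimental arm rehearses the identical test every day.* The Phoenix list gives no position for Shoulder Flexion, the exercise enters only in Phase 3, and the instructed frequency is not compulsory.
- *That a count of home sessions measures the bias.* At the instructed frequency, weeks 10 to 20 give 11 × 5 = 55 sessions. That is exposure, not degrees, and it depends on when Phase 3 starts and on adherence.
- *That the effect would leave no trace.* QuickDASH does not use the device, so a flexion gain without a matching QuickDASH gain would be a warning, although it could not isolate the effect.
- *That the primary outcome is affected.* The documents do not say how the motion part of the Constant Score is taken.

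The reply does not remove the difference in familiarity with the interface, or the absence of any rule on what patients see.

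**Conclusion.** The concern holds as a possible bias in one secondary outcome. Flexion is measured in both arms as an exercise on the device that only the experimental arm uses at home, and the assessment procedure does not keep the app's targets, feedback and stars from the patient. This could favour the experimental arm at week 20.

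The documents do not allow the amount to be computed, and they do not show that any bias would occur. The conclusion rests on two assumptions: that the usual display is visible during assessment, or at least not excluded, and that familiarity with it affects performance on an active movement. The sample size of 68 is unaffected, since it is based on the Constant Score. The change is worth making because it is cheap, but the point is minor.

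**What to change.** In Section 13.1.3, keep Phoenix as the measuring instrument and add two rules for every assessment in both arms:
1. The patient does not see the app's targets, stars or feedback. For example, the tablet faces the assessor, who gives the same standard verbal instruction for the five repetitions.
2. The recorded value is the maximum angle over the five repetitions, whether or not the app counts that repetition as correct.

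This fits the existing procedure, in which the investigator already asks for the repetitions and reads the values later in the portal. It needs no new instrument, visits or patients, and turning the tablet does not depend on the app being able to hide its display.

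The cost is that the assessor must cue each patient verbally, and posture is then controlled by that instruction and not by the app. Some general familiarity with the device will remain.

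An added unrecorded practice set is not recommended. It would mean more active elevation at the week-6 visit, close to the precaution on active elevation in the Phase 2 table.

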13.1.1 Constant Score

The Constant Score is a functional assessment score specific to the shoulder region, that varies between 0 and 100 points, being 100 the best score possible. This total score is distributed in subjective assessments of pain and activities of

daily living (15 and 20 points, respectively) and objective measures of shoulder range of motion and strength (40 and 65 points, respectively).⁵⁵

The Constant Score is the most used instrument to assess the shoulder in Europe and its psychometric properties prove it to be a valid, reliable and responsive measure.^{56,57} Kukkonen et al. (2013)⁵⁶ determined that the Minimum Clinical Important Difference - MCID of the Constant Score for patients with arthroscopically treated rotator cuff repairs was of 10.4 points.

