Gentle pendulum exercises for three to five minutes every one to two hours	

Table 2. Phase 1 of the rehabilitation program (weeks 2 to 4)

Rotator cuff repair program: Phase 1 - Immobilization period	
Goals	Precautions
Control pain and swelling	
Protect the rotator cuff repair	Do not lift the operated arm
Protect wound healing	
Prevent shoulder stiffness	
Intervention	
Conventional PT group 2 weeks 2 face-to-face sessions per week	Experimental Group 2 weeks: 1 face-to-face session per week Daily sessions with SWORD Phoenix
Ice pack application on the shoulder for 15 minutes to reduce pain and swelling	Intervention of the Control Group + SWORD Phoenix Exercises: - Scapula Elevation - Scapula Protraction - Scapula Retraction - Elbow Flexion - Forearm Supination - Forearm Pronation - Pendular Exercises
Active mobilization exercises of the scapula, elbow, forearm and hand	
Pendular exercises	
Drainage massage, when needed	

Table 3. Phase 2 of the rehabilitation program (weeks 5 to 7/9)

Rotator cuff repair program: Phase 2 - passive mobilization	
Goals	Precautions
Maintain integrity of the repair Avoid overstress healing tissue Gradually increase soft passive range of motion Diminish pain and inflammation Prevent muscular inhibition Begin early shoulder motion Reach 120° passive scapular mobility Reach 40° passive external rotation Reach 120° passive shoulder flexion	No active elevation for the first six weeks No lifting of objects No excessive stretching or sudden movements No supporting of body weight by hands Avoid resisted exercises and exercises in coronal plane abduction No mobilization of the shoulder for flexion on the scapular plane (20° to 30°) between 60° and 110° if rotator tear suture Avoid shoulder external rotation until the 8 th week if shoulder instability
Intervention	
Conventional PT group 5 weeks 3 face-to-face sessions/week	Experimental Group 5 weeks:2-2-2-1 face-to-face sessions* daily sessions with SWORD Phoenix

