Ice pack application on the shoulder for 15 minutes to reduce pain and swelling Sub-maximal isometric strengthening: internal and external rotation at neutral Start soft passive ROM movements: - Limit lying internal rotation to 30° in the scapular plane (20° to 30°) - Lying external rotation to 60° in the scapular plane (20° to 30°) - Lying shoulder flexion in the scapular plane (20° to 30°) When passive ROM starts to improve, progress to soft active-assisted exercises (lying flexion, external and Internal rotation) Exercises: Ball squeezes, AROM for elbow, forearm and hand, scapular elevation and retraction	Intervention of the Control Group + SWORD Phoenix Exercises: - Scapula Elevation - Scapula Protraction - Scapula Retraction - Elbow Flexion - Forearm Supination - Forearm Pronation

Legend: * progressing to 1 session/week when possible

Patients may progress to the next phase after completing all passive range of motions of the shoulder described with no pain associated.

Table 4. Phase 3 of the rehabilitation program (weeks 8-10 to 12-14)

Rotator cuff repair program: Phase 3 - active movements	
Goals	Precautions
Maintain integrity of the repair and avoid overstress healing tissue Gradually increase to assisted and active range of motion Progressive scapular stability Progressive functional training Restore full shoulder motion	Respect previous precautions Do soft strengthening exercises under 1,5kg Weight training precautions Avoid excessive force on the shoulder
Intervention	
Conventional PT group 5 weeks 3 face-to-face sessions/week	Experimental Group 5 weeks: 1 face-to-face session/week daily sessions with SWORD Phoenix

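### The week-6 visit calls for best-effort active abduction and a Constant strength test while Table 3 advises against coronal-plane abduction and resisted exercises, and the plan does not resolve the conflict

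*Combined protocol and SAP*

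**What the plan says.** Section 13.2 sets the first post-operative assessment at week 6 and asks for the Constant Score, the QuickDASH and "Shoulder range of motion (as described for the baseline assessment". The baseline procedure in Section 13.1.3 measures active movement, seated, in scapular-plane elevation, flexion, abduction and external rotation. Each is done five times at the patient's best effort. For abduction the instruction is to "have the patient actively open the arm as much as possible", with the elbow straight.

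Section 13.1.1 says the Constant Score has objective parts for "range of motion and strength (40 and 65 points, respectively". It gives no position, plane or load for the strength test and no rule for scoring an omitted part.

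Table 3 in Section 14 covers Phase 2, weeks 5 to 7/9. Its precautions include "No active elevation for the first six weeks No lifting of objects" and "Avoid resisted exercises and exercises in coronal plane abduction". The only resistance work it lists for the shoulder is "Sub-maximal isometric strengthening: internal and external rotation at neutral". Section 14 also says that "these protocols can be tailored to the patient's specific needs", on the judgement of the surgeon and the physical therapist.

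**The concern.** An assessor who follows Section 13.2 at week 6 asks a patient with a recent repair for maximal active abduction and a strength effort. Table 3 tells the therapist to avoid this kind of loading in the same weeks. An assessor who follows Table 3 departs from the assessment schedule with no written authority and no scoring rule. The group-blinded assessors of Section 12 are left to choose.

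The first consequence is for safety. The background text stresses that failed healing and re-tears are common and that protection and movement must be balanced. Section 15 builds its safety monitoring around rehabilitation sessions rather than assessment visits.

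The second consequence is for the data. If some assessors leave out strength and others do not, week-6 Constant totals would mix complete and incomplete scores.

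**Working it through.** The plan states no figure on this point, so the check compares the texts and the timeline.

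**1. Which phase contains week 6?** The inputs are the headings of the phase tables and the face-to-face session schedule in Section 14.

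| Phase | Earliest printed weeks | Normal schedule | Visit inside on both |
|---|---|---|---|
| 2, passive mobilization | 5–7 | 5–9 | week 6 |
| 3, active movements | 8–12 | 10–14 | week 12 |
| 4, strengthening | 13–18 | 15–20 | week 16 |

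Phase 3 starts in week 8 at the earliest, so week 6 is in Phase 2 on either schedule.

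**2. Required tests against Phase 2 precautions.**

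- *Abduction.* Section 13.1.3 lists it separately from scapular-plane elevation and flexion, so the natural reading is the coronal plane. The set-up steps in that section call all four movements exercises. Table 3 says to avoid exercises in that plane. This is the clearest conflict.
- *Strength.* Measuring strength needs effort against resistance. Table 3 says to avoid resisted exercises and lists only the isometric rotation quoted above. The conflict is in kind. Its degree cannot be judged, because the manoeuvre is not described.
- *Flexion and scapular-plane elevation.* Active elevation is barred for the first six weeks. Six completed weeks is 6 × 7 = 42 days. No visit window is given, so a visit held during the sixth week (days 36 to 42) would fall inside the ban and one held after day 42 would not.
- *External rotation.* Table 3 restricts it only with shoulder instability, until week 8, so it is not part of this point.

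**3. Is there an exemption?** The tailoring clause concerns the rehabilitation protocols. Neither Section 13 nor Section 14 reduces the week-6 assessment.

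**4. What could an omitted strength part do to a total?** The four printed Constant parts add to 15 + 20 + 40 + 65 = 140, against a stated maximum of 100. If the maximum and the other three parts are right, strength carries 100 − 15 − 20 − 40 = 25 points. That is a ceiling on what one omitted part could remove, not an expected loss. It exceeds the 10.4-point MCID, so complete and incomplete totals should not be pooled.

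**5. What remains after the change?** Constant totals up to week 20 are planned at baseline and weeks 6, 12, 16 and 20, which makes 5. Without week 6, 5 − 1 = 4 remain. The 3x2 ANOVA in Section 16 has two groups and therefore three time levels, which it does not name. Four totals are enough for three levels.

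**The case against.** The strongest reply is that Table 3 sets principles for repeated therapy sessions, that avoiding is softer than the outright prohibitions beside it, and that one visit with five unloaded repetitions is not a training load. The Constant Score guideline cited in Section 13.1.1, not available here, may define a safe test and the scoring of omitted parts. Calling the movements exercises may only describe a portal step.

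Much of this stands. It rules out calling the visit a breach of an absolute bar, and it makes the strength half less certain than the abduction half. It does not remove the conflict, because no text says that assessments fall outside the precautions.

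A reader might also infer that active flexion and scapular-plane elevation are ruled out at week 6, because Table 3 adds: "No mobilization of the shoulder for flexion on the scapular plane (20° to 30°) between 60° and 110° if rotator tear suture". The documents do not support that firmly. The same table sets a 120° passive flexion goal, so the line is unclear drafting, and the ban on active elevation ends at six weeks.

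A reader might further infer that later visits need the same treatment, since Phase 3 keeps the earlier precautions and limits strengthening to under 1.5 kg. That does not follow. Phase 3 itself prescribes progress to full range in all planes with increasing abduction. It also lists wall push-ups although Phase 2 bars taking weight through the hands, so the carry-over is not literal. Phase 4 has a parallel 3.0 kg limit. A rule discarding totals from load-limited tests would therefore also remove the week-16 and week-20 totals, and with them the primary endpoint.

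**Conclusion.** The point holds for week 6 only. Two parts of the plan give incompatible instructions for active abduction, and for strength on the assumption that any strength test needs resisted effort. The scope is 1 of 4 scheduled post-operative visits up to week 20. At that visit it covers 1 of 4 range-of-motion movements and the strength part of the Constant Score, in both arms.

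No effect on results is quantified. It would be tempting to infer bias or damage to the primary analysis, but the documents do not support either. The assessment procedure is the same in both arms, and Section 16 bases the main comparisons on change from baseline to week 20. The repeated-measures ANOVA is touched only if week 6 is one of its unnamed time levels, and the documents give no ground for dictating which three levels to use. Severity is low. The case for acting is patient safety at little cost.

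**What to change.** Amend Section 13.2, for the week-6 visit only:

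1. Omit active coronal-plane abduction, the Constant strength test, and any Constant range-of-motion item that needs active coronal-plane abduction.
2. Hold the visit after six completed weeks (after day 42), so that the ban on active elevation has ended.
3. Report the week-6 Constant Score by component, without a total, and use no week-6 total in the repeated-measures ANOVA.

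Leave the week-12, 16 and 20 assessments as planned.

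The cost is the week-6 Constant total and the week-6 abduction value. The Constant range-of-motion component may also be incomplete at that visit, since the protocol does not list its items. Abduction is not a named outcome in Section 5, and the baseline-to-week-20 analyses of the Constant Score, QuickDASH and flexion are unchanged.
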